6.4 Combinations of medications and treatments

All comorbid medications and treatments during the study period are to be documented. If a new systemic cGVHD treatment is initiated during the study period it will be considered as initiation of a new cGVHD treatment and will be considered as a failure of BN101/belumosudil treatment.

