6.4.1 Corticosteroids

Therapeutic doses of corticosteroids are to be collected throughout the study. After ≥2 weeks of BN101/belumosudil use, the dose of corticosteroids may be reduced at the discretion of the investigator.

A transient increase in corticosteroid dose (no more than 1 mg/kg/day prednisone equivalent) is permitted during cGVHD episodes, but this dose must be adjusted to the pre-enrollment dose level within 6 weeks. If the dose remains elevated for more than 6 weeks, it will be considered a BN101/belumosudil treatment failure. The occurrence of more than 2 episodes of cGVHD requiring an increase in corticosteroid dose during the first 6 months of BN101/belumosudil treatment will also be considered a BN101/belumosudil treatment failure.

If the planned response assessment falls during a cGVHD episode of treatment, this response assessment will still be performed as planned, but the assessment will not be included in the primary efficacy analysis.

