6.4.2 Systemic cGVHD Therapies

Per the eligibility criteria, subjects receiving standard of care systemic cGVHD therapies such as calcineurin inhibitors (tacrolimus, cyclosporine), sirolimus, MMF, methotrexate, rituximab or ECP, may be enrolled if they have been on a stable dose/schedule. During the study treatment period, it is permissible to continue cGVHD treatment as described above at doses/regimens that have stabilized prior to enrollment, but it is not permissible to increase the dosage of these medications unless the increase in dosage is used only to maintain the current therapeutic level of the medication (e.g., to maintain the current blood concentration). Doses and schedules of these therapies will be collected throughout the study and changes will be documented.

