10.6.2.2 Secondary Efficacy Endpoints

Secondary endpoints are as follows:

- DoR, defined as the time from the first evaluation of CR or PR to the confirmed occurrence of cGVHD progression. For subjects who had not experienced cGVHD progression at the end of the study, the date of their last objective evaluation was used as the DoR censoring date.
- Changes in the Lee Symptom Scale Score: Analyses will include:
 - Number of subjects with a \geq 7 point reduction
 - Number of subjects with a \geq 7 point reduction on 2 consecutive assessments
 - Duration of a \geq 7 point reduction
- Response by organ system: The response assessment for the nine individual organs (Skin, Eyes, Mouth, Esophagus, Upper GI, Lower GI, Liver, Lungs, and Joints and fascia).
- Number and percentage of subjects who have a best response of PR and number and percentage of subjects who have a best response of CR.
- Change in corticosteroid dose
- The prednisone equivalent dose of corticosteroids (mg/kg/day) during the study will be analyzed.
- Change in calcineurin inhibitor dose.
- FFS, FFS is defined as the absence of cGVHD treatment change, non-relapse mortality and recurrent malignancy. Median FFS (from first dose of BN101/Belumosudil) and landmark FFS at 1 year(if applicable) will be analyzed.
- OS, defined as time from first dose of BN101/belumosudil to the date of death due to any
 cause.
- Changes in cGVHD global severity rating using the Clinician-Reported Global cGVHD Activity Assessment
- Changes in symptom activity using the cGVHD Activity Assessment Patient Self-Report

Descriptive statistics will be provided for all secondary endpoints.

For DoR (only for subjects determined to have CR and/or PR), FFS, and OS, the median, first quartile, third quartile, and their two-sided 95% CIs were calculated using the Kaplan-Meier method, and survival curves were plotted.

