5.1. Efficacy Endpoints

5.1.1. Primary Efficacy Endpoints

The primary efficacy endpoint is the overall response rate (ORR) as assessed by the investigators based upon the 2014 NIH Consensus Development Project on Clinical Trials in cGVHD.

Response is assessed using individual scores from ten systems (Skin, Eyes, Mouth, Esophagus, Upper GI, Lower GI, Liver, Lungs, Joints and Fascia and Global Severity Rating (GSR)). Response is assessed with respect to the baseline (Cycle 1, Day 1 (C1D1)) cGVHD assessment. The overall response at each assessment time point will be categorized as Complete Response (CR), Partial Response (PR), or Lack of Response (LR), where LR includes the response status of unchanged, mixed, or progression as defined in [Table 1](#).

The ORR is defined as the proportion of patients with a best response meeting the overall response criteria assessment of CR or PR at any post-baseline response assessment.

If a treated patient is lost to follow up without response assessment, this patient will be counted as a non-responder. Any response on and after new systemic cGVHD treatment will be censored as non-response.

Table 1: cGVHD Response Definitions

| Response | Definition |
|------------------------|---|
| Complete Response (CR) | Resolution of all manifestations of cGVHD in each organ or site. |
| Partial Response (PR) | Improvement in at least one organ or site without progression in any other organ or site. |
| Lack of Response (LR) | |
| Mixed (LR-M) | Complete or partial response in at least one organ accompanied by progression in another organ* |
| Unchanged (LR-U) | Outcomes that do not meet the criteria for complete response, partial response, progression or mixed response |
| Progression (LR-P) | Progression in at least one organ or site without a response in any other organ or site |

* Considered progression for the purposes of analysis

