Response assessment by physician for the nine individual organs (skin, eyes, mouth, esophagus, upper GI, lower GI, liver, lungs and joints and fascia) plus global severity rating will be collected in eCRF.

Time to Response (TTR)

TTR is defined as the time from first treatment to the time of first documentation of response.

Time to Next Therapy (TTNT)

TTNT is defined as the time from first treatment to the time of new systemic cGVHD treatment, censored by last response assessment or long term follow up assessment, which ever is the latest and available.

Corticosteroid Dose

Corticosteroid doses will be presented as mg/kg/day prednisone equivalent dose. If a patient is not using prednisone as the systemic corticosteroid, then the prednisone dose equivalent will be determined according to following conversion ratios:

1mg prednisone is equivalent to:

- 4mg Hydrocortisone
- 0.8mg Methylprednisolone
- 0.15mg Dexamethasone

- 1mg Prednisolone
- 0.8mg Triamcinolone

Transient increase in corticosteroid dosing (not exceeding 1mg/kg/day prednisone equivalent) is permitted for the treatment of cGVHD flare, but dose must be reduced back to the pre-enrollment dose within 6 weeks. If the dose remains elevated for more than 6 weeks, this will be considered a BN101/belumosudil treatment failure. More than 2 episodes of cGVHD flare requiring increased corticosteroid in the first month of BN101/belumosudil treatment will also be considered a BN101/belumosudil treatment failure.

Calcineurin Inhibitor (CNI) Dose

CNI includes systemic tacrolimus and cyclosporine.

Failure Free Survival (FFS)

FFS is defined as the absence of new cGVHD systemic therapy, non-relapse mortality and recurrent malignancy (e.g. underlying disease) and is censored by last response assessment or long term follow up assessment, whichever is the latest and available.

Overall Survival (OS)

OS is defined as time from first dose of BN101/belumosudil to the date of death due to any cause.

Change in cGVHD severity using the Clinician-Reported Global cGVHD Activity Assessment

The Clinician-reported global cGVHD Activity Assessment is a 0-10 point numeric rating scale with a score 0 indicating “cGVHD symptoms not at all severe” and a score of 10 being “most severe cGVHD symptoms possible”. The activities are assessed on Day 1 of each cycle from Cycle 1 Day 1 to EOT.

Change in symptom activity using the cGVHD Activity Assessment Patient Self-Report

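### The SAP's FFS and ORR rules react only to new systemic cGVHD therapy, so an increase in background therapy outside protocol 6.4.2 triggers no event, and the protocol and SAP definitions of FFS are not reconciled

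*SAP*

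**What the plan says.** Both documents build FFS from three components and agree on two of them: death without relapse, and return of the malignancy. They differ on the third. Protocol 10.6.2.2, with the same wording in 7.1.2, says: "FFS is defined as the absence of cGVHD treatment change, non-relapse mortality and recurrent malignancy". Neither section says what counts as a treatment change. SAP 5.1.2 says: "FFS is defined as the absence of new cGVHD systemic therapy, non-relapse mortality and recurrent malignancy". The SAP gives no reason for the different wording.

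For ORR, SAP 5.1.1 has one rule that removes responses: "Any response on and after new systemic cGVHD treatment will be censored as non-response".

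Protocol 6.4.2 lets patients continue stable background systemic cGVHD therapy, but "it is not permissible to increase the dosage of these medications unless the increase in dosage is used only to maintain" the existing therapeutic level. The same section provides the data: "Doses and schedules of these therapies will be collected throughout the study and changes will be documented".

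**The concern.** The trial has one arm, and its purpose is to show that results in Chinese patients agree with KD025-213. With no control group, all response and failure-free time is read as the effect of study drug. Stronger background immunosuppression is a competing explanation. The protocol recognises this by barring increases, but the SAP does not say what happens to the endpoints if the bar is broken.

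Only an event is missing from the rules, and no credit is withheld anywhere to offset it. Any error therefore goes one way, towards a higher ORR and longer FFS.

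**Working it through.** **Step 1. Follow one patient through the SAP.** Suppose a patient has not responded, the MMF dose is raised for worsening cGVHD, and a PR is recorded two visits later. No new drug is started.

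- ORR (SAP 5.1.1, 8.4.1): the removal rule needs new systemic therapy, so the patient is a responder.
- FFS (SAP 5.1.2): no new therapy, death or relapse has occurred, so the patient stays failure-free.
- DoR (SAP Table 2): events are deterioration or lack of response, new systemic therapy, and death. The increase is not an event.
- TTNT (SAP 5.1.2): the event is new systemic treatment only.
- CNI dose (SAP 8.4.2): reductions and discontinuations are tabulated, increases are not. Sirolimus, MMF, methotrexate and ECP have no planned on-study dose analysis.
- Per-protocol set (SAP 7, 8.4): it may drop the patient if the increase is classed as a major deviation, but it is used only for the primary endpoint.

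Corticosteroids are a separate case. SAP 5.1.2 calls certain steroid increases a treatment failure but does not link that label to ORR, DoR or FFS. Protocol 6.4.1 says of a visit during flare treatment that "this response assessment will still be performed as planned, but the assessment will not be included in the primary efficacy analysis"; the SAP has no matching rule. The documents also differ on the window for repeated flares (first 6 months in the protocol, first month in the SAP). These passages must be reconciled too.

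**Step 2. Reference figure.** The sample size of 30 has no statistical derivation, so there is no design figure to reproduce. The comparator ORR in protocol 1.4.2 does reproduce: 48/66 = 72.7%, Clopper-Pearson 95% CI 60.4 to 83.0.

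**Step 3. Size for ORR.** One patient is 1/30 = 3.3 points. Assume 22/30 responders, close to the comparator (0.727 × 30 = 21.8). Let k be the number whose first response follows a non-permitted increase; k is assumed, since the documents give no frequency. The last column drops those patients, as the per-protocol set might.

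| k | Counted as non-response | Exact 95% CI | Dropped instead |
|---|---|---|---|
| 0 | 22/30 = 73.3% | 54.1 to 87.7 | 22/30 = 73.3% |
| 1 | 21/30 = 70.0% | 50.6 to 85.3 | 21/29 = 72.4% |
| 2 | 20/30 = 66.7% | 47.2 to 82.7 | 20/28 = 71.4% |
| 3 | 19/30 = 63.3% | 43.9 to 80.1 | 19/27 = 70.4% |

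Dropping patients removes only part of the effect, because they also leave the denominator.

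**Step 4. Size for FFS.** For illustration, take exponential FFS with the 10.7-month median that protocol 1.4.2 reports for KD025-208. The hazard is h = ln 2/10.7, and 12-month FFS is exp(−12h) = 46.0%. Let q be the assumed probability of a non-permitted increase by 12 months, acting as an independent hazard h₂ = −ln(1 − q)/12. Then 12-month FFS becomes 46.0% × (1 − q), and the median becomes ln 2/(h + h₂).

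| q | 12-month FFS | Median (months) |
|---|---|---|
| 0 | 46.0% | 10.7 |
| 5% | 43.7% | 10.0 |
| 10% | 41.4% | 9.4 |
| 15% | 39.1% | 8.8 |
| 20% | 36.8% | 8.3 |

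If patients whose background therapy is raised also tend to fail soon afterwards by the SAP's own events, the loss at a given q is smaller than shown.

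**The case against.** A reader might infer that the protocol makes every treatment change an FFS event, that its wording was meant to catch background increases, and that the SAP departs from it. The documents do not support that.

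- The protocol never defines the term. Read literally, it would turn a permitted steroid taper into a failure, although protocol 3.3 lists steroid and tacrolimus reductions as examples of clinical benefit.
- Protocol 6.4 expressly treats the start of new systemic therapy as failure of study drug, and 6.4.1 adds certain steroid increases. A background increase is barred but never called a failure. The SAP may therefore be making an undefined term workable, a task protocol 10.1 leaves to it.
- The ORR rule is not a departure. Protocol 10.6.2.1 counts CR or PR at any post-baseline assessment with no removal rule, so the SAP's rule is already the stricter one.
- The effect on ORR is limited. A patient who responded before the increase remains a responder under any version, and median time to first response in the KD025-213 200 mg QD group was 4.4 weeks.
- The documents do not show KD025-213's FFS and response rules. A stricter primary definition here could make the comparison less like-for-like.

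All of this stands, and it argues against replacing the primary definitions. It does not close the gap. The FFS wordings still differ without explanation, and long-term follow-up in protocol 4.3.6 asks about any change in cGVHD therapy, which is wider than new therapy. No SAP rule addresses the increase. The deviation listing and per-protocol set may reveal it for ORR but give FFS no protection.

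**Conclusion.** The point holds as an unreconciled definition and an unhandled event. It does not show that the SAP breaks a clear protocol rule. The direction is certain: adding the missing event can only lower ORR and FFS or leave them unchanged.

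The size is unknown. It is 3.3 ORR points for each patient whose first response follows such an increase, and about 2 to 9 points on 12-month FFS if 5% to 20% of patients have one. Those figures rest on assumed counts, an assumed 22/30 base, and an exponential model with independent hazards. With one to three patients the ORR shift is 3.3 to 10 points, well inside the sampling interval at n=30. The analysis is descriptive, so no error rate or power is affected. The point should be settled before lock, when the rule can be written without reference to results.

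**What to change.** Before database lock:

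1. Reconcile the FFS definition in protocol 7.1.2 and 10.6.2.2 with SAP 5.1.2, and state what treatment change means for the analysis, excluding tapers and topical or organ-specific therapy.
2. Keep the new-systemic-therapy version of FFS and the present ORR rule.
3. Add a pre-specified FFS analysis in which the treatment event is new systemic cGVHD therapy or an increase of background systemic cGVHD therapy not made to maintain its current level.
4. Add an mITT sensitivity analysis of ORR that counts responses on or after such an increase as non-response and keeps the patient in the denominator.

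The cost is SAP wording, two extra analyses, and a medical review of dose changes by someone who does not see the response data. The dose changes are already collected under protocol 6.4.2. The documents do not say that the reason for an increase is recorded, so some queries may be needed. Appendix 1 collects these therapies until 28 days after the last dose; after that, FFS would rely on the telephone contacts about every 12 weeks. The resulting figures may be slightly less favourable.

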4.3.6 Long-Term Safety Follow-Up

Subjects who terminate study treatment early before the end of the main study will be contacted by telephone by the study center approximately every 12 weeks to confirm their survival, any changes in cGVHD treatment, and any antitumor therapy until the end of the main study (see Section 3.5).

Subjects who have not yet experienced cGVHD progression at the end of the study, and in the judgment of the investigator, the benefits of continued dosing outweigh the risks, may submit a written request and, upon approval by the sponsor's Medical Director and documentation of the subject's willingness to continue the treatment, the sponsor will continue to provide BN101/belumosudil medication at no cost until cGVHD progression, intolerable toxicity, initiation of a new cGVHD therapy, recurrence of hematological neoplasm, loss to follow-up, withdrawal of consent, or death, etc., whichever occurred first. During this period, subjects will return to the study center in accordance with their clinical practice, and the study will continue to collect SAEs, study drug use, and survival (or can be contacted by phone). In addition, SAEs for this group of subjects will need to be collected up to 28 days (±7) after the last dose or the initiation of new cGVHD therapy.

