- 13. The end of the main study is defined as 12 months after the last subject was enrolled. Subjects who have not yet experienced cGVHD progression at the end of the main study, and in the judgment of the investigator, the benefits of continued dosing outweigh the risks, may submit a written request and, upon approval by the sponsor's Medical Director and documentation of the subject's willingness to continue the treatment, the sponsor will continue to provide BN101/belumosudil medication at no cost until cGVHD progression, intolerable toxicity, initiation of a new cGVHD therapy, recurrence of hematological neoplasm, loss to follow-up, withdrawal of consent, or death, etc., whichever occurred first. For subjects assessed as "Lack of Response Mixed" and "Lack of Response Progression" (see the main body of the protocol), if the investigator believed that these subjects could continue to benefit from treatment with BN101/belumosudil, the treatment may be continued after a written application was submitted, and approval from the Sponsor's Medical Director as well as documentation of the subject's willingness to continue treatment was obtained.
- 14. On the first day of cycle 7 (C7D1) and all subsequent odd cycles (C7D1, C9D1, C11D1, etc.), subjects will receive 2 cycles of study drugs and 2 copies of drug dairy and return to the clinic for efficacy and safety assessment every other treatment cycle, as well as dispense/collect study drugs until the end of the main study.
- 15. Subjects will return to the clinic for EOT assessment within 7 days after the final administration of the study drug or at the end of the main study (only for subjects who have not discontinued the study drug at the end of the main study). Subjects who withdraw from the trial early should also return to the clinic for EOT assessment. End-of-treatment visits are also required at the end of the main study if subjects have not discontinued study drug at the end of the main study. EOT

Cycle Day (d)	Screening/Baseline		Cycle 1		Cycle 2~N ^{13,14}	End of Treatment (EOT) ¹⁵	28-Day Follow-Up ¹⁶	Long Term Follow-Up ¹⁷
Assessment	-14 ~ -1	-7 ~ -1	C1D1	C1D8、15 (±3)	CxD1 (±3)	(+7)	(土)	At the end of treatment or at the end of the main study

visits should be done prior to new treatment.

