The study enrollment period is estimated to be 6 months. 6 months after the last patient enrollment, the database will be locked and the primary analysis will be conducted. After primary analysis, all patients will be followed up for additional 6 months and a follow up analysis will be conducted 12 months after the last patient enrollment.

Eligible patients who have signed informed consent will be enrolled to receive BN101/belumosudil (every 28-day cycle) until cGVHD progression, intolerable toxicity, initiation of a new cGVHD therapy, recurrence of hematological neoplasm, loss to follow-up,

withdrawal of consent, or death, whichever occurs first. During study, concomitant treatment with standard of care systemic cGVHD therapies such as corticosteroids, calcineurin inhibitors (tacrolimus, cyclosporine), sirolimus, MMF, or extracorporeal photopheresis (ECP), are permitted as long as the patient has been on a stable dose / regimen of these per the eligibility criteria. Initiation of new systemic cGVHD therapy while on study is not permitted. Response criteria will be assessed after cycles 1, 2, 3 and 4 and then after every other cycle thereafter (i.e. on Day 1 of Cycle 2, 3, 4, 5, 7, 9, 11 etc). For patients assessed as "Lack of Response - Mixed" and "Lack of Response - Progression" [Evaluated by the investigator based on the National Institutes of Health (NIH) Consensus Development Project on Criteria for Clinical Trials in cGVHD(2014), hereinafter referred to as the NIH Consensus Criteria (2014)], if the investigator believed that these patients could continue to benefit from treatment with BN101/belumosudil, the treatment may be continued after a written application was submitted, and approval from the Sponsor's Medical Monitor as well as documentation of the patient's willingness to continue treatment was obtained. For patients who did not achieve any response after 12 cycles of BN101/belumosudil treatment, they should discontinue the study medication and withdraw from the study if in the investigator's judgment there is no evidence of clinical benefit (e.g., improvements in organ score, improvements in Lee symptom scores, reductions of corticosteroid/tacrolimus doses). For patients whose cGVHD has not progressed at the time of discontinuation of the study treatment and who come off study for reasons other than AEs should be tapered off BN101/belumosudil by reducing the dose every other week (200mg QD → 200mg QOD → discontinue).

5. Study Endpoints

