The best response (CR, PR) for the nine individual organs plus global severity rating will be summarized. Time to response at the organ level will also be evaluated. Descriptive statistics and plots of cumulative number and percentage of responders over time will be provided. Two series of percentages will be presented:

- With total number of patients in mITT with involvement of the given organ at baseline as denominator
- With numbers of patients in the responder population with involvement of the given organ at baseline as denominator

Time to Response (TTR)

Descriptive statistics and plots of cumulative number and percent of responders over time will be provided. TTR analyses will only be conducted for the responder population.

Time to Next Therapy (TTNT)

TTNT will be analysed by the Kaplan-Meier survival method as well as the landmark analysis at 3, 6, 9, and 12 months.

Corticosteroid Dose

Corticosteroid doses will be presented as prednisone equivalent dose. Descriptive statistics for the mITT population, responder / nonresponder populations will be provided for:

- Systemic corticosteroid dose over time
- Change and percent change from baseline (C1D1) to the greatest corticosteroid dose reduction during BN101/belumosudil treatment period
- Number and percentage of patients who reduced systemic corticosteroid dose during BN101/belumosudil treatment period
- Number and percentage of patients who ever discontinued systemic corticosteroid usage for over 28 days during BN101/belumosudil treatment period

The above analyses will be censored on or after new systemic cGVHD treatment.

Calcineurin Inhibitor (CNI) Dose

CNI includes systemic tacrolimus and cyclosporine. Descriptive statistics will be provided for:

- Number and percentage of patients who reduced CNI dose during BN101/belumosudil treatment period
- Number and percentage of patients who ever discontinued CNI during BN101/belumosudil treatment period

Failure Free Survival (FFS)

Kaplan-Meier plots, descriptive statistics of FFS and landmark FFS at 3, 6, 9, and 12 months will be provided. In addition, analyses for the three components of FFS will also be provided.

Overall Survival (OS)

Kaplan-Meier plots, descriptive statistics of OS and landmark OS at 3, 6, 9, and 12 months will be provided.

Change in cGVHD severity using the Clinician-Reported Global cGVHD Activity Assessment

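### FFS and TTNT have no common cut-off for events and censoring; if events count to the data cut, Kaplan-Meier at the primary analysis is biased slightly downward, mainly at 9 months

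*SAP*

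**What the plan says.** - **Censoring.** SAP 5.1.2 states that FFS "is censored by last response assessment or long term follow up assessment, whichever is the latest and available". TTNT is "censored by last response assessment or long term follow up assessment, which ever is the latest and available".
- **Events.** SAP 5.1.2: "FFS is defined as the absence of new cGVHD systemic therapy, non-relapse mortality and recurrent malignancy". No last date for counting events is given. SAP Table 2 re-dates certain events that follow missed assessments, but only for duration of response.
- **Assessment schedule.** SAP 4 places response assessments "on Day 1 of Cycle 2, 3, 4, 5, 7, 9, 11 etc", in 28-day cycles. Protocol Appendix 1, note 14, says that from Cycle 7 patients "return to the clinic for efficacy and safety assessment every other treatment cycle".
- **Follow-up calls.** Protocol 4.3.6: "Subjects who terminate study treatment early before the end of the main study will be contacted by telephone". Calls are about 12 weeks apart. For an event-free patient on drug the censoring rule therefore reduces to the last response assessment.
- **Capture of failures.** An end-of-treatment visit is due within 7 days of the last dose and before any new treatment (Protocol 4.3.4; Appendix 1, note 15). Deaths up to 28 days after the last dose are reported within 24 hours (Protocol 8.7.2).
- **Timing.** SAP 4: "6 months after the last patient enrollment, the database will be locked and the primary analysis will be conducted". SAP 4 estimates enrolment at 6 months. Protocol 10.5 instead places the lock 2 to 3 months after the last subject completes 6 cycles.
- **Outputs.** SAP 8.4.2: "Kaplan-Meier plots, descriptive statistics of FFS and landmark FFS at 3, 6, 9, and 12 months will be provided". TTNT has the same landmarks. Neither is confined to one of the two analyses.

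**The concern.** Kaplan-Meier assumes that a censored patient has the same prospects as those who remain at risk. Here the censoring date can depend on the outcome. Take two on-drug patients last assessed at week 24, with the data cut at week 31. One starts a new therapy at week 29 and is counted at risk, and as an event, at week 29. The other is still well at week 31 and is removed at week 24. Between week 24 and the cut, the risk set keeps the patient who fails and drops the one who does not. The hazard is overstated and the curve drops too far. This is a bias, not only lost precision.

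The study has no hypothesis test (SAP 6). Consistency with KD025-213 will be judged from estimates and curves, and an error that always runs in one direction makes the Chinese patients look slightly worse than they are.

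**Working it through.** The documents give no planned FFS or TTNT figure, so there is none to reproduce.

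**Inputs**
- Assessments: weeks 4, 8, 12, 16, then 24, 32, 40, 48 (28-day cycles; C5D1 to C7D1 = 2 × 28 = 56 days).
- Potential follow-up at the primary analysis: 6 to 12 months (6-month enrolment, cut 6 months after the last patient), taken as uniform.
- Median FFS: 10.7 months, the KD025-208 figure in Protocol 1.4.2. This and the exponential shape are assumptions; medians of 6 to 24 months were also run.
- n = 30. All patients are on drug until failure (assumption, varied below).
- One month = 365.25/12/7 = 4.348 weeks, so landmarks fall at weeks 13.0, 26.1, 39.1 and 52.2.

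**True values.** S(t) = exp(−λt), with λ = ln 2/(10.7 × 4.348) = 0.0149 per week. At 3/6/9/12 months: 82.3/67.8/55.8/46.0%.

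**3 months.** Minimum follow-up is 26.1 weeks, so nobody is censored before week 24. Bias: none.

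**6 months, by hand.** Patients whose cut falls between weeks 26.1 and 32 are censored at week 24 if event-free.
- Their share is (32 − 26.1)/(52.2 − 26.1) = 0.226; the other 0.774 are unaffected.
- Of the affected patients, only those who fail before their cut stay at risk. The cut averages week 29.05 and the interval's midpoint is week 25.05, 4 weeks apart, so that fraction is about 1 − exp(−0.0149 × 4) = 0.058.
- The risk set shrinks to 0.774 + 0.226 × 0.058 = 0.787 of its proper size, and the hazard is inflated by 1/0.787 = 1.27.
- Excess cumulative hazard from week 24 to 26.1: 0.0149 × 2.09 × 0.27 = 0.0084.
- Estimate: 67.8% × exp(−0.0084) = 67.2%, a bias of about half a point.

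**Simulation (400,000 patients, events counted to the cut)**

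| Landmark | True | SAP censoring | Event-free censored at cut | Events and censoring both stop at last assessment |
|---|---|---|---|---|
| 3 months | 82.3% | 82.3% | 82.3% | 82.3% |
| 6 months | 67.8% | 67.3% | 67.8% | 67.8% |
| 9 months | 55.8% | 52.8% | 55.9% | 56.0% |

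The mean gap from censoring to cut is 4.0 weeks. Over medians of 6 to 24 months the bias is −0.3 to −0.8 point at 6 months and −2.0 to −3.3 points at 9.

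**At n = 30 (5,000 trials).** The mean 9-month estimate is 52.9% under the SAP rule and 56.0% when censored at the cut, with a standard deviation of about 10 points. The SAP-rule estimate was the lower one in 95% of trials.

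**12 months.** The last possible assessment is week 48, and with 6 to 12 months of follow-up nobody is still at risk at week 52.2 under either rule. The n = 30 averages (39% and 47.5%) should not be read as a bias estimate.

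**Other follow-up, median 10.7 months**
- 8 to 14 months (about what Protocol 10.5 implies): 0 at 6 months and −1.0 point at 9.
- 6 to 18 months (the synopsis's study duration of about 2 years, less 12 months after last enrolment, leaves up to 12 months of enrolment): −0.3 to −0.4 point at 6 months and −1.2 at 9.

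**Patients off drug without an FFS event.** With 20 to 40% off drug by 6 months, the 9-month bias is −3.7 to −4.0 points if all their failures are known to the cut, and −1.7 to −2.5 if failures are learned only at the 12-weekly calls.

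**The case against.** The strongest reply is that the SAP does not specify a biased analysis. It never says that events count to the data cut; it is silent. If events were counted only to each patient's last assessment, there would be no bias through 9 months. That stands, and the conclusion is conditional on the reading. But the event definitions have no upper date, failures are captured off schedule, and the only re-dating rule is for duration of response. Counting every recorded failure is what a programmer would do by default.

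Three stronger readings are tempting and are not supported:
- *All the landmarks are biased.* Three months is unaffected and 6 months barely so.
- *Twelve-month FFS will be badly understated.* At the primary analysis that estimate is unreliable whichever rule is used. Protocol 10.6.2.2 makes the one-year landmark conditional on being applicable. At the follow-up analysis, on-drug patients have a uniform end-of-treatment visit with a response assessment (Protocol 4.1 and 4.3.4), which largely closes the gap.
- *FFS at the primary analysis decides the bridging question.* Neither document says so. The primary endpoint is ORR; FFS and TTNT are secondary and descriptive.

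It is also fair to say that the rule has a second half, the long-term follow-up contact. For off-drug patients whose failures are learned only at calls, events and censoring stop together and those patients add no bias. This reduces the overall effect but does not remove it. Finally, a 3-point shift is under a third of the standard deviation at n = 30, so it would rarely change an interpretation by itself.

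**Conclusion.** The point holds conditionally. The SAP sets a censoring date for event-free patients and no matching limit for events. If events are counted to the cut, FFS and TTNT at the primary analysis are biased downward: none at 3 months, about 0.5 point at 6 and about 3 points at 9. At 9 months this falls to about 1 point if follow-up is 8 to 14 or 6 to 18 months. These figures rest on exponential FFS with a median of 10.7 months, uniform accrual and all patients on drug until failure; with some patients off drug the 9-month figure ranges from about 1.7 to 4.0 points. No bias figure is claimed for 12 months at the primary analysis. The direction is systematic and the remedy is simple, so the change is worth making, as a modest improvement rather than a major correction.

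**What to change.** In SAP 5.1.2, for FFS and TTNT:
1. Set one data cut-off date that applies to both events and censoring. SAP 4 and Protocol 10.5 time the primary analysis differently, so reconcile them when setting it.
2. Confirm status at that date for each event-free patient (alive, no new systemic cGVHD therapy, no relapse) and censor at the cut-off.
3. If status cannot be confirmed, close follow-up for all patients, with or without an event, at the last assessment due on or before the cut-off, and count events only to that date.

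In SAP 8.4.2, report the 12-month landmarks from the follow-up analysis only.

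Moving the censoring date to the last drug-dispensing or diary record would add little, because from Cycle 7 those fall at the same 8-weekly visits.

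The cost is a few lines of SAP text and one status query per event-free patient before lock, at most 30. In the simulation, censoring at a confirmed cut-off gave 55.9% at 9 months against a true 55.8%. The fallback in item 3 also removes the bias through 9 months, but its curve is flat after week 48.
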